1.4.3 Rationale for the Dosage and Treatment Period

Our chosen dose 1×10^6 cells/kg weekly x 4 weeks is within the dosing parameters of previous trials. In trials of MSCs in pediatric GVHD, doses as high as 8×10^6 cells/kg/dose were given up to twice per week for four weeks. [51] The rate of

administration (for patients < 35 kg, total infusion over 60 minutes, and for children ≥ 35 kg, 4-6 ml/minute via infusion pump) is also consistent with prior pediatric administration in patients with GVHD. [51]

2 STUDY OBJECTIVES AND DESIGN

2.1 Study Objectives:

2.1.1 Primary Objective:

The primary objective is to examine the safety and tolerability of infusions of fresh bone marrow-derived MSCs in the treatment of children and young adults with moderate to severe IBD.

2.1.2 Secondary objectives:

1. Examine the effects of 4 infusions of MSCs on clinical measures of disease activity in patients, using clinical indices, as well as endoscopic scores (if applicable), histologic scores, and MR enterography when available.
2. Examine inflammatory and immunologic effects of MSC infusions on peripheral and intestinal mucosal biomarkers including, but not limited to serum CRP, fecal calprotectin, anti-HLA antibodies, and viral specific T-cell activity before and after treatment.

2.2 Study Design

This study is a pilot phase 1 treatment protocol for subjects with moderate to severe CD or UC who have failed to respond to or are intolerant of a biologic. Patients must have had a flexible sigmoidoscopy, colonoscopy or MR enterography within 2 months of enrollment, demonstrating active inflammatory disease.

Two types of patients will be enrolled:

- Moderate to severely active CD subjects (defined in Section 2.4)
- Moderate to severely active UC subjects (defined in Section 2.4)

At the beginning of the trial, a history and physical examination will be obtained, and documentation of baseline co-variates[52]:

CD:

- age
- gender

BMSCs

- ethnicity
- history of abdominal surgery
- duration of time with diagnosis
- age at diagnosis
- disease location
- history of failed biologic use
- history of stricturing/penetrating disease
- positive family history of IBD
- history of perianal disease
- severity and phenotype (Montreal classification for adults, or Paris classification for children)

UC:

- age
- gender
- ethnicity
- age at diagnosis
- history of failed biologic use
- duration of time since diagnosis
- positive family history of IBD)

During the course of the patient's treatment with MSCs, standard of care will be administered by the treating physician, at his/her discretion. There are no specific or "antidotal" therapies. Thus, any toxicity that arises during a patient's participation in this treatment will be managed with supportive measures at the discretion of the treating physician.

Three young adult patients (ages 17≤22 years) will be enrolled, staggered by at least 7 days between patients, and each monitored for toxicity over a period of 73 days. A fixed dose will be studied: 1×10^6 cells/kg administered intravenously (IV) weekly for 4 consecutive weeks. Infusions are administered over the first 28 days, followed by a 45 day monitoring period. The primary outcome is regimen-related toxicity, defined in section 5. Toxicity will be scored as a binary variable indicating occurrence or non-occurrence over a monitoring interval from the start of MSC therapy to 45 days after the last infusion. Based on the planned administration schedule, the total toxicity monitoring period will have duration $28 + 45 = 73$ days.

If we observe no severe (grade 3 or worse) adverse events in the young adult cohort, we will wait a minimum of 45 days before beginning to enroll 3 more patients, ages 12≤16 years (pediatric cohort). If we observe a severe (grade 3 or worse) adverse event occurring at any time from the start of therapy to 45 days following the last MSC administration in the young adult cohort we will stop the study. If we observe no severe adverse events attributable to MSC administration in the young adult cohort but a

severe (grade 3 or worse) adverse event occurring at any time from the start of therapy to 45 days following the last MSC administration in the pediatric cohort we will stop the study. A maximum of 6 patients will be enrolled. Assuming an accrual rate of 3-4 patients per year, it is anticipated that it will require at least 18 – 24 months to accrue all 6 patients. With the additional 24 months of follow up to evaluate efficacy endpoints noted in Section 2, the anticipated trial duration will be about 48 months.

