Study Design: This study is a pilot phase 1 study of patients with moderately to severely active Crohn Disease (CD) and ulcerative colitis (UC) (≥ 18 years, Mayo score: ≥ 6 or CDAI: > 220 ; < 18 years, Pediatric Crohn's Disease Activity Index (PCDAI) > 30) or Pediatric Ulcerative Colitis Activity Index (PUCAI) > 34). [1] [2] A fixed dose will be studied: 1×10^6 cells/kg administered intravenously (IV) weekly for 4 consecutive weeks, with the option of an additional 4 weeks of treatment, at the discretion of the principal investigator. The primary outcomes are regimen-related toxicity, defined in section 5. Toxicity will be scored as a binary variable indicating occurrence or non-occurrence over a monitoring interval from the start of MSC therapy to 45 days after the last infusion. Based on the planned administration schedule of 4 weeks, the total toxicity monitoring period will have duration $28 + 45 = 73$ days. If additional weekly doses are administered, the safety assessment phase will be 45 days after the last dose given.

Three young adult patients (ages 17≤22 years) will be enrolled, staggered by at least 7 days, and monitored for toxicity over a period of 73 days. Infusions are administered over the first 28 days, followed by a 45 day monitoring period. If we observe no severe (grade 3 or worse) adverse events in the young adult cohort, we will wait a minimum of 45 days after the last MSC administration before beginning to enroll 3 more patients, ages 12≤16 (pediatric cohort). If we observe a severe (grade 3 or worse) adverse event occurring at any time from the start of therapy to 45 days following the last MSC administration in the young adult cohort we will stop the study. If we observe no severe adverse events attributable to MSCs in the young adult cohort but a severe (grade 3 or worse) adverse event occurring at any time from the start of therapy to 45 days following the last MSC administration in the pediatric cohort we will stop the study. A maximum of 6 patients will be enrolled. Assuming an accrual rate of 3-4 patients per year, it is anticipated that it will require at least 18-24 months to accrue all 6 patients.

Eligibility

This protocol allows for the treatment of both male and female pediatric and young adult patients, between the ages of 12 ≤ 22 years, with active moderate to severe CD or UC, who have failed to respond to, or are intolerant of, biologic therapy.

Inclusion criteria

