1.4 Scientific Rationale and Clinical Justification

1.4.1 Rationale for the study of BMSCs in Pediatric IBD

Pediatric IBD is a chronic, life-long condition beginning in childhood, characterized by relapsing inflammation of the gastrointestinal tract. Inflammation is thought to be mediated by T cells, macrophages, and dendritic cells that produce downstream cytokines. Despite the many therapeutic advances in the treatment of IBD, many patients still suffer with refractory disease. Children with IBD are typically exposed to multiple medications over years, and many suffer with associated serious side effects.

According to 2009 US Census data, inflammatory bowel diseases (IBD) (i.e. Crohn's disease and ulcerative colitis) affect about 1.2 million Americans. Of these, 62,000 are children (38,000 CD and 23,000 UC). Thus, 5% of all IBD cases in the USA are of pediatric age (<20 years). This qualifies drugs to treat pediatric UC and pediatric CD as orphan indications.

(http://www.accessdata.fda.gov/scripts/opdlisting/oopd/OOPD_Results_2.cfmIndex_Number=340911) Further, while there are options for the treatment of IBD in adults, other than corticosteroids, infliximab (Remicade) and adalimumab (Humira) are FDA-approved for the treatment of moderate to severe pediatric CD. Infliximab has orphan drug designation to treat pediatric UC. Certolizumab pegol, methotrexate, 6MP, and 5-ASA products are NOT FDA approved for use in children with UC or CD.

(<http://www.accessdata.fda.gov/scripts/cder/drugsatfda/>)

The scientific rationale for investigating the use of MSCs in IBD patients is based on known properties of inflammatory and immune modulation and enhancement of tissue repair. This is not a first-in-human study and there is now a sizable body of evidence that this intervention is safe when used in people ≥ 18 years of age. However, the safety of MSCs has not been yet demonstrated in children with IBD. While children cannot be treated as "small adults", this is not an intervention that is expected to have substantially different impact on children than adults because metabolic differences are not a concern for this intervention. CD and UC are considered similar enough that efficacy in children has been extrapolated from adults in past trials of drugs used to treat IBD.

Therefore, there is an urgent medical need to evaluate novel therapies such as MSCs in pediatric IBD since:

- 1). Children with refractory IBD have few well-studied treatment options.

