Our cell therapy product consists of allogeneic mesenchymal stromal cells manufactured from an eligible normal donor. We have a CNMC IRB-approved protocol (Pro00006717) that provides a mechanism for the use of excess bone marrow obtained from healthy donor bone marrow harvests. Up to 100 mL of marrow will be obtained from Lonza (Walkersville, MD) under informed consent and transported to Children's National Health System in a validated process at 2-8°C. The donor will meet the eligibility requirements as described in 21 CFR parts 1271 Subpart C. Testing (Table 1) will be performed using FDA-approved, cleared and/or licensed kits by Lonza within 7 days of collection of the marrow for manufacturing. Manufacturing will commence within 24 hours of marrow collection. Risk factors will be assessed by taking a clinical history, clinical examination, and by use of a standard questionnaire for blood donors.

Table 1:	Test
Chagas Disease	
Hepatitis B Surface Antigen	
Hepatitis B Core	
Hepatitis C Core	
HIV 1 and 2	
TAQ Screen MPX (HBV, HCV, HIV-1 group M RNA, HIV-1 Group O)	
NAT HCV	
NAT West Nile Virus	
Serological Test for Syphilis	
CMV	
HTLV-1	

This would not be a first-in-human study and there is now a sizable body of evidence that this intervention is safe when used in people ≥ 18 years of age. However, the safety of MSCs has not been yet demonstrated in

children with IBD. Safety and dosing may not be extrapolated from adult studies, as classic pharmacokinetic monitoring to document equivalent exposure-response is not feasible with cell therapies.

1.4.2 PLAN OF STUDY:

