3 STUDY AGENT

3.1 Preparation Administration, and Dosage

On the day of each infusion, the following procedures/assessments will be performed:

- MSCs will be thawed, harvested, counted, the viability will be determined, and appropriate samples will be sent for other release testing (including sterility). Vital signs (heart rate, blood pressure, respiratory rate, and temperature) will be measured within 15 minutes prior to the infusion (time 0) and then every 5 minutes during the infusion. If vital signs are normal after three 5-minute checks, they will be checked every 15 minutes during the remainder of the infusion, and then at 30 and 60 minutes after the infusion for 1 hour.
- Patients will be monitored according to institutional standards for administration of blood products and at a minimum will be monitored according to below:
 - Patients should remain in the clinic for at least one hour
 - Patients should remain on continuous pulse oximetry for at least 30 minutes

- Vital signs should be monitored at the end of the infusion then at 30 and 60 minutes
- Per institutional guidelines, pre-medication, consisting of oral acetaminophen (10-15 mg/kg/dose, max 650 mg) and diphenhydramine (0.5-1 mg/kg/dose, max 50 mg), will be administered at least 30 minutes prior to the infusion.
- No other medications should be given during the infusion, unless determined medically necessary by the treating physician.
- Supplemental oxygen will be kept by the bedside at all times.
- MSCs suspended in Plasmalyte A (multiple electrolyte injection) will be given as an IV infusion using weight-based dosing. We plan to infuse $1-4 \times 10^6$ cells per mL, not to exceed 240 mL. With a mean weight of 40 kg, the infusion volume would be 40-120 mL.
- Cells will be infused on Day 0 followed by repeat infusions weekly over a total of 4 weeks. An additional 4 weekly doses may be infused at discretion of physician. An attempt will be made to administer repeat infusions from the same initial donor, but administration of MSCs from another donor is permitted if same-donor cells are unavailable. Tracking of donor sample identification information will be performed for each sample.

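### The protocol sets a minimum interval between young adult patients but none between the three children, so the one-event stopping rule is not guaranteed to act before all three have been dosed

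*Protocol*

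**What the plan says.** The stagger appears in the synopsis (Study Design), section 1.4.2 and section 2.2, each time for the three young adults only. In section 2.2 they "will be enrolled, staggered by at least 7 days between patients, and each monitored for toxicity over a period of 73 days"; in the synopsis they "will be enrolled, staggered by at least 7 days, and monitored for toxicity over a period of 73 days".

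The pediatric cohort is described in the same three places and in section 7.1.4. Its only timing control in section 2.2 is a gate in front of the whole cohort: if the young adults have no severe event, the study waits at least 45 days before "beginning to enroll 3 more patients, ages 12≤16 years (pediatric cohort". After that, a single grade 3 or worse event from the start of therapy to 45 days "following the last MSC administration in the pediatric cohort we will stop the study". No section sets an interval between children or asks for review of one child before the next starts. Section 10.2 gives the Data Review Committee serious events, unanticipated problems, deaths and an annual safety review, but no review between patients.

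On the evidence in children, section 1.4.1 says that "the safety of MSCs has not been yet demonstrated in children with IBD" and, at its end, "Safety and dosing may not be extrapolated from adult studies".

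On the schedule, section 3.1 says: "Cells will be infused on Day 0 followed by repeat infusions weekly over a total of 4 weeks". Up to 4 further weekly doses are optional.

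**The concern.** A rule that stops the study after one event limits the number of patients exposed only if patients start at different times. The protocol secures this for the young adults and leaves it open for the children, the group in which it calls safety undemonstrated. If children happened to start close together, an early severe reaction in the first could come when the other two had already been dosed. What is at stake is first exposure of up to two further children that a between-patient interval would have prevented.

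Spacing of enrollment is a matter for the protocol, which already specifies it for one cohort. It is not a detail normally left to a statistical analysis plan.

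**Working it through.** **Inputs.** Accrual of 3-4 patients per year, maximum 6, in two cohorts of 3 (section 2.2). Stagger of at least 7 days, young adults only (section 2.2). Infusions on days 0, 7, 14 and 21 (sections 3.1 and 3.8), so 3 × 4 = 12 planned infusions in the pediatric cohort. Toxicity window 28 + 45 = 73 days (section 2.2).

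**1. The protocol's own figure.** 6/4 × 12 = 18 months and 6/3 × 12 = 24 months. The stated 18-24 months reproduces. The mean gap between patients is 365/4 ≈ 91 days to 365/3 ≈ 122 days.

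**2. Exposure when the first child has an event.** The table counts children started and infusions given by the day of the event. It assumes that the stagger separates first infusions and that the study stops on the day of the event. The 7-day column carries over the young adult value for comparison only.

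| Day of event in first child | Same-day starts: children / infusions | Starts on days 0, 7, 14: children / infusions |
|---|---|---|
| 0-6 | 3 / 3 | 1 / 1 |
| 8 | 3 / 6 | 2 / 3 |
| 15 | 3 / 9 | 3 / 6 |
| 22 | 3 / 12 | 3 / 9 |
| 30 | 3 / 12 | 3 / 11 |

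With same-day starts the number of children exposed is always 3, but stopping still withholds 12 − 3 = 9 infusions for an event on days 0-6, 6 on day 8 and 3 on day 15. With a 7-day stagger, a child is kept unexposed only for events before day 14. Infusions are reduced until day 35, when the third child's last dose falls (14 + 21).

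**3. How likely are close starts?** The documents give no distribution of gaps. Assume exponential gaps at rate r per year:

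- P(one gap < 7 days) = 1 − exp(−7r/365.25): 0.056 at r = 3 and 0.074 at r = 4.
- P(at least one of two gaps < 7 days) = 1 − (1 − 0.0559)² = 0.109 to 1 − (1 − 0.0738)² = 0.142, so 11-14%.
- P(both gaps < 7 days) = 0.0559² to 0.0738², so about 0.3-0.5%.
- P(at least one of two gaps < 73 days), by the same formula: 0.70 to 0.80. Overlapping toxicity windows are therefore likely even where close starts are not.

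**4. How often would the rule be called on?** For an assumed chance p per child of an event that triggers it, the rule triggers with probability 1 − (1 − p)³: 0.27, 0.49 and 0.66 for p = 0.1, 0.2 and 0.3. Fully sequential treatment gives the upper bound on what spacing could save. Expected children exposed would be 1 + (1 − p) + (1 − p)² = 2.71, 2.44 and 2.19, against 3 with same-day starts.

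**The case against.** The strongest reply is that the children already have a safeguard that the young adults lack. All three young adults must first be free of grade 3 or worse events, and then at least 45 days must pass. Section 1.4.2 says that enrolling young adults first was specified in the FDA IND review. Section 1.4.1 also says that the intervention is not expected to act very differently in children, and section 1.4.2 cites higher and more frequent dosing in pediatric GvHD. Monitoring and stopping criteria at each infusion (sections 3.1 and 5.6) apply to every patient. At the stated accrual, a 7-day interval would usually change nothing.

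Much of this stands. A reader might infer that the stopping rule cannot limit exposure among the children at all. That is not so, because even with same-day starts it withholds the remaining infusions. A reader might also infer that the protocol plans simultaneous starts, or that children will queue until the gate opens. The protocol says neither, and no section describes a waiting list. Eligibility works against a long queue: active disease must be documented within the preceding 2 months (section 2.6.1), and screening falls in the 30 days before the first dose (section 3.6). Some queuing is possible and would raise the 11-14%, but by an unknown amount.

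The reply does not close the gap. The gate separates the two cohorts, not one child from another. Per-infusion monitoring protects the child being infused, not the next one. Section 9.1 allows three business days for reporting unexpected grade 3 events, so closely spaced starts could outrun the rule.

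**Conclusion.** The point holds as an asymmetry in the written safeguards. A minimum interval exists for young adults and none for children, although the protocol calls safety in children with IBD undemonstrated. Followed as written, the plan does not guarantee that the one-event rule can act before all three children have had a first infusion.

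The probability is low and the consequence limited: an 11-14% chance of at least one gap under 7 days, and well under 1% that both are. These rest on exponential gaps at 3-4 patients per year and ignore queuing. In the worst case, an event on days 0-6, 3 children rather than 1 are exposed. Because the population is vulnerable and the change cheap, it should be made, but it does not undermine the design.

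**What to change.** Reconcile the pediatric-cohort text in the synopsis (Study Design) and sections 1.4.2, 2.2 and 7.1.4 with the stagger text in the synopsis and sections 1.4.2 and 2.2, so that between-patient staggering also covers the pediatric cohort. State whether the interval runs between enrollments or between first infusions. Its length is a clinical decision for the sponsor; the 7 days used above is only the protocol's own young adult value.

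The cost is about one sentence in each place, in an amendment. At the young adult value the added delay is at most 2 × 7 = 14 days for the cohort, and usually none with a mean gap of 91-122 days. The gain is limited too: at that value, spacing spares a child a first dose only when the first child's event comes before day 14.

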2.2.1 Primary Endpoint

Safety and tolerability of the administration of human allogeneic bone marrow-derived stromal cells to children and young adults with IBD, measured by the frequency of any SAEs, AEs and/or early treatment discontinuations.

2.2.2 Secondary Endpoints

- Magnitude of change in PCDAI, PUCAI, CDAI to baseline, reporting the average decline and 95% confidence limit.
- Changes in laboratory parameters indicating inflammation or immunogenicity(i.e. C-reactive protein, fecal calprotectin, anti-HLA antibodies, and viral specific T-cell activity))
- When available, magnitude of endoscopic improvement, as assessed by change in endoscopic scores (Simple Endoscopic Score Crohn's Disease [SES-CD] for CD or Endoscopic Sub Score within the Mayo Score for UC) relative to baseline, reporting the average decline and 95% confidence intervals.

2.2.3 Exploratory Endpoint

- Blood, urine, saliva, and stool will be collected for evaluation of biomarkers

2.3 Study Population

This treatment protocol allows for the treatment of both male and female young adults and children between the ages of 12 years and 22 years with a diagnosis of moderate to severe CD or UC who have failed or are intolerant of biologic therapy.

Subjects with moderate-to-severe CD are defined as patient with a PCDAI score > 30 with visually active CD at the time of endoscopy/colonoscopy, or signs of inflammation on MR enterography, within 2 months of enrollment.

Subjects with moderate-to-severe active UC are defined as a patient with a PUCAI score >34, and visually active mucosal disease by colonoscopy or flexible sigmoidoscopy within past 2 months.

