- Had bowel surgery other than perianal procedures (fistulotomy, seton placement, abscess drainage) within 3 months of enrollment.
- Has uveitis
- Has known pulmonary disease, excluding mild intermittent asthma

Primary Endpoints

- Safety and tolerability of the intravenous administration of human allogeneic bone marrow-derived MSCs to children and young adults with IBD, measured by the frequency of any SAEs, AEs and/or early treatment discontinuations.

Secondary Endpoints

- Magnitude of decrease in clinical index (for young adults we will use the CDAI and Mayo, and for children the PCDAI and PUCAI) relative to baseline, reporting the average decline and 95% confidence limit.
- Changes in biomarkers of inflammation and immunogenicity (i.e. C-reactive protein, fecal calprotectin, anti-HLA antibodies, viral-specific T cell activity)
- Where available, magnitude of endoscopic improvement, as assessed by change in endoscopic scores (Simple Endoscopic Score Crohn's Disease [SES-CD] for CD or Endoscopic Sub Score within the Mayo Score for UC) relative to baseline, reporting the average decline and 95% confidence intervals [3, 4].

Exploratory Endpoints

Blood, urine, saliva, and stool will be collected for evaluation of biomarkers

Accrual Period: Estimated accrual of 3-4 patients per year for 18-24 months

Study Duration: Approximately 48 months, including follow up

TABLE OF CONTENTS

1	BACKGROUND AND RATIONALE	8
1.1	Inflammatory Bowel Disease:	8
1.3	Description of the Study Agent/Intervention.....	9
1.4	Scientific Rationale and Clinical Justification	11
1.4.1	Rationale for the study of BMSCs in Pediatric IBD	11
1.4.2	PLAN OF STUDY:	13
1.4.3	Rationale for the Dosage and Treatment Period	14
2	STUDY OBJECTIVES AND DESIGN.....	15
2.1	Study Objectives:.....	15
2.1.1	Primary Objective:	15
2.1.2	Secondary objectives:	15
2.2	Study Design	15
2.2.1	Primary Endpoint	17
2.2.2	Secondary Endpoints	17
2.2.3	Exploratory Endpoint	17
2.3	Study Population.....	17
2.4	Recruitment Plan	18
2.5	Informed Consent.....	18
2.6	Eligibility criteria	19
2.6.1	Subject Inclusion Criteria	19
2.6.2	Subject Exclusion Criteria	19
3	Study Agent.....	20
3.1	Preparation Administration, and Dosage.....	20
3.2	Assessment of Subject Compliance	21
3.3	Concomitant Medications and Procedures.....	22
3.4	Prohibited Medications and Procedures	22
3.5	Study Schedule.....	22
3.6	Table 1: Protocol of Events.....	22
3.7	Baseline assessment/screening.....	25
3.8	Treatment Phase (Day 0, 7, 14, 21)	25

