This is a pilot phase 1 treatment protocol for subjects with moderate to severe CD or UC who have failed or are intolerant of one biologic. Subjects must have had a flexible sigmoidoscopy or colonoscopy or MR enterography within 2 months of enrollment, demonstrating active inflammatory bowel disease. Subjects with moderate to severe CD are defined differently in children and adults. In patients <17 years of age, moderate to severe CD will be defined as having a Pediatric Crohn Disease Activity Index (PCDAI) score of > 30 (range 0-100) and subjects with moderate to severe UC are defined as a patients with a Pediatric Ulcerative Colitis Activity Index (PUCAI) score of >34 (range 0-85). In patients \geq 18 years of age, moderate to severe CD will be defined as a CDAI of \geq 220 (range 0-600), and moderate to severe UC defined as a Mayo score of \geq 6 (range 0-12). In our study, at the specification of the FDA IND review, a young adult cohort will be enrolled first and monitored for toxicity. A pediatric cohort will only begin to enroll if there are no serious adverse events observed in the young adult cohort. Subjects will be closely monitored both by the study team to detect and evaluate adverse events (AEs), serious adverse events (SAEs), and toxicity requiring discontinuation of the intervention.

Three young adult patients (ages $17 \leq 22$ years) will be enrolled, staggered by at least 7 days. A fixed dose will be studied: 1×10^6 cells/kg administered intravenously (IV) weekly for 4 consecutive weeks. Infusions are administered over the first 28 days, followed by a 45 day monitoring period. Our chosen dose (1×10^6 cells/kg weekly for a duration of 4 weeks) is within the dosing parameters of previous trials. In trials of MSCs in pediatric GvHD, doses as high as 8×10^6 cells/kg/dose were given up to twice per week for four weeks. [51] The rate of administration (for patients < 35 kg, total infusion over 60 minutes, and for ≥ 35 kg, 4-6 ml/minute via infusion pump) is also consistent with prior pediatric administration in patients with GvHD. [51]

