2.6 Eligibility criteria

2.6.1 Subject Inclusion Criteria

- For the young adult cohort, patients must be ages 17 ≤22 years
- For the pediatric cohort, patients must be ages 12 ≤16 years
- Patients must have moderate-severely active CD or UC (defined in section 2.3), and documented active disease on flexible sigmoidoscopy, colonoscopy or MR enterography within the preceding 2 months.
- Patients who have failed or are intolerant of biologic therapy. Specifically, the patient will have recurrence or persistence of active disease despite current or past treatment with a biologic. At the time of enrollment, study subjects may be currently receiving 5-aminosalicylates, corticosteroids (≤ 20 mg daily or up to 0.5 mg/kg/day if weight <40 kg), methotrexate, 6MP/azathioprine, or a biologic (either as monotherapy or in combination). During the treatment phase, if the treating physician thinks that a medication dose should be lowered to avoid side effects, this should be recorded.
 - Patient or parent/guardian capable of providing informed consent.
-

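### Three conflicting definitions of moderate-to-severe disease: Section 2.3, which the inclusion criteria invoke, has no adult index, so young adults enter on a paediatric scale but are analysed on an adult one.

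*Protocol*

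**What the plan says.** Three places in the Protocol define moderate-to-severe disease.

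- **Synopsis, Study Design.** The rule splits at 18: "≥ 18 years, Mayo score: ≥ 6 or CDAI: > 220 ; < 18 years, Pediatric Crohn's Disease Activity Index (PCDAI) > 30", with PUCAI >34 as the ulcerative colitis (UC) counterpart below 18.
- **Section 1.4.2.** The paediatric rule stops a year earlier: "In patients <17 years of age, moderate to severe CD will be defined as having" PCDAI >30, with PUCAI >34 for UC. The adult rule starts at 18, with CDAI ≥220 or Mayo ≥6.
- **Section 2.3.** There is no age split: "Subjects with moderate-to-severe CD are defined as patient with a PCDAI score > 30", and PUCAI >34 for UC. CDAI and Mayo do not appear. For UC it also asks for "visually active mucosal disease by colonoscopy or flexible sigmoidoscopy within past 2 months"; MR enterography is accepted only in the Crohn's disease (CD) sentence.

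Section 2.6.1 and the matching synopsis criterion settle which of these is operative: "Patients must have moderate-severely active CD or UC (defined in section 2.3"). Section 2.2 instead points twice to Section 2.4, which is the Recruitment Plan and holds no definition.

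For the secondary endpoint, the synopsis assigns the index by cohort: "for young adults we will use the CDAI and Mayo, and for children the PCDAI and PUCAI". The young adult cohort begins at 17. Section 2.2.2 lists PCDAI, PUCAI and CDAI for clinical change but not the Mayo score. The footnote to Table 1 names all five indices without an age split.

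**The concern.** An entry criterion should give the same answer whichever page the screener opens. Here a 20-year-old is screened on PCDAI or PUCAI by following the cross-reference, and on CDAI or Mayo by following the synopsis. Nothing in the document says that a score above one threshold implies a score above the other.

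The endpoint is the average decline from baseline with a 95% confidence limit. If a patient is admitted on one scale and change is taken on another, the baseline on the outcome scale need not have met any activity threshold. With three patients per cohort, one patient admitted under a disputed definition is a third of that cohort's average.

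**Working it through.** No sample size, power or error rate is involved, so the check is to apply each written rule to every age from 12 to 22 and compare it with the index assigned for change.

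| Age | Synopsis, Study Design | Section 1.4.2 | Section 2.3 (operative) | Index for change (synopsis, Secondary Endpoints) |
|---|---|---|---|---|
| 12–16 | PCDAI >30 / PUCAI >34 | PCDAI >30 / PUCAI >34 | PCDAI >30 / PUCAI >34 | PCDAI, PUCAI |
| 17 | PCDAI >30 / PUCAI >34 | no rule | PCDAI >30 / PUCAI >34 | CDAI, Mayo |
| 18–22 | CDAI >220 / Mayo ≥6 | CDAI ≥220 / Mayo ≥6 | PCDAI >30 / PUCAI >34 | CDAI, Mayo |

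1. **Ages 12–16.** All three definitions agree, and entry and change use the same scale.
2. **Age 17.** Two definitions cover this age. Both give a paediatric index, while the cohort's change is measured on an adult one, so the scales differ under each.
3. **Ages 18–22.** Under the synopsis or Section 1.4.2, entry and change match. Under Section 2.3 they do not. The two adult rules differ from each other only at a CDAI of exactly 220.
4. **Number affected.** Under Section 2.3 the mismatch covers the whole young adult cohort: 3/6 = 50% of the maximum enrolment.

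**Is a baseline on the outcome scale available?** Table 1 schedules disease activity at screening, on Day 0 and at every later visit, and its footnote includes CDAI and Mayo. A CDAI baseline is therefore planned.

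Mayo is less secure. Appendix 4 gives four items scored 0–3, for a maximum of 4 × 3 = 12, and one item is endoscopic. Section 3.9 says endoscopy is done for clinical purposes only, and Section 3.7 allows that scores from an outside facility may be unavailable. Without that item, let S be the sum of the other three items (0–9). The full score then lies between S and S + 3. Against the threshold of 6:

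- S ≥ 6: met whatever the endoscopic item is.
- S ≤ 2: cannot be met, since 2 + 3 = 5.
- S = 3, 4 or 5: undetermined.

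The same gap affects change, because no endoscopy is scheduled after entry.

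**Related inconsistencies.**

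- *MR enterography in UC.* Section 2.6.1 lists it for CD and UC together, and Section 1.4.2 does likewise. Section 2.3 names only colonoscopy or flexible sigmoidoscopy for UC.
- *Worsening criterion.* Section 6 defines worsening by PCDAI >50 or PUCAI >65 only, although the synopsis follows young adults on adult indices.

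**The case against.** The strongest reply is that Section 2.3 is simply an incomplete copy. The synopsis and Section 1.4.2 agree on CDAI or Mayo from 18, the intent is recoverable, and Table 1 collects everything. Change from baseline needs a baseline on the same scale; it does not need that score to have been the entry criterion. The primary endpoint is safety, and the stopping rules in Section 7 use adverse events, not activity scores.

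Much of this stands, and it limits the point. A reader might go further in several directions that the document does not support:

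- *That four definitions conflict.* Only three places define the disease. Section 2.6.1 is a pointer, and Section 2.2 is a wrong pointer.
- *That 17-year-olds have no entry rule.* That is true of Section 1.4.2 alone. The synopsis and Section 2.3 both cover them.
- *That no adult-scale baseline will exist.* Table 1 plans one; only the full Mayo score is in doubt.
- *That the chance of enrolling a 17-year-old can be stated.* The document gives no age distribution. If each patient had a 10% to 30% chance of being 17, the chance of at least one in three would run from 1 − 0.9³ = 27% to 1 − 0.7³ = 66%; equal weight on ages 17–22 gives 1 − (5/6)³ = 42%. Nothing here depends on this, since Section 2.3 affects all three young adults at any age.
- *That the MR enterography wording makes UC entry impossible.* Both conditions can be met together, and read jointly the endoscopy requirement governs. It needs clarifying, no more.

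The reply does not remove the eligibility problem. The inclusion criterion names Section 2.3, and a footnote on what is measured does not set who may enter.

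**Conclusion.** The point holds as an internal inconsistency in the eligibility rule. The operative definition has no adult index and conflicts with the synopsis and Section 1.4.2 for ages 18–22. At age 17, entry and outcome scales differ under every definition that covers that age. Taken literally, this affects 3 of at most 6 patients. The conclusion rests only on reading the cross-reference in Section 2.6.1 as written and on the synopsis assignment of indices by cohort.

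The consequence is for eligibility and for the secondary clinical-index endpoint, chiefly where that index is Mayo and the endoscopic item is missing. A reader might infer that the safety conclusion is compromised; it is not, because neither the measurement of toxicity nor the stopping rules use these scores. The point should be corrected, but it ranks below the defects that must be resolved before the trial can be interpreted. Which threshold is right is not judged here.

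**What to change.** Make Section 2.3 the single definition and have every other section refer to it. In that section:

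- name one index per cohort and disease, used for both entry and change, consistent with the assignment in the synopsis Secondary Endpoints and explicit for 17-year-olds;
- use one inequality at CDAI 220;
- state how Mayo is scored, for entry and for change, when no endoscopic subscore is available, without adding endoscopies;
- state whether MR enterography alone suffices for UC.

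Then align the synopsis design text and Section 1.4.2, add Mayo to Section 2.2.2, and correct the Section 2.2 pointer from 2.4 to 2.3. The worsening criterion in Section 6, which names only PCDAI and PUCAI, must be reconciled with the indices used for young adults; its content is a clinical matter for the investigators.

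The cost is protocol wording only: no extra patients, visits or procedures.
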